14. STATISTICAL CONSIDERATIONS

14.1. *Study Design and Objectives*

The study is designed as multi-center, open label study, designed to confirm the safety and the efficacy of ¹³C-urea breath test using the **BreathID® Hp and BreathID® Hp Lab Systems** in pediatric subjects and confirm the efficacy of the respective means of breath collection, the nasal cannula and breath collection bags, in this population compared to *stool antigen* testing. A central lab will analyze the stool specimens. Children, that cannot inflate the breath collection bags, may perform UBT only with **IDkit:Hp One** nasal cannula. All children will be exposed to non-radioactive ¹³C-urea and citric acid. Subjects will be enrolled on a walk-in basis. Subjects will be treated only based on the established methods

Exalenz Bioscience Ltd.	Last update on: Mar. 12, 2017
Study Title: Clinical Study to Confirm Safety and Accuracy in Detection of H. pylori with ¹³C-Urea Breath Test using the BreathID® Hp and BreathID® Hp Lab Systems in the Pediatric Population	Protocol Number: PED-HP-0616B Version 2.0
Document No.: CSD00092	Page 44 of 59

used in the local routine clinical practice and the investigator and treating physician will remain blinded to the breath test results until the end of the study.

14.2. *Endpoints*

14.2.1. *Primary Endpoint: Safety*

Adverse event rate: The safety of the ¹³C-urea/citric acid solution has been previously established in adults and in children in literature⁽¹⁻³⁾. Any adverse event (whether related or not) will be recorded. There are no safety concerns and no adverse events anticipated for the breath tests.

14.2.2. *Secondary Endpoints: Efficacy*

1. Overall agreement in diagnosis (presence/absence of *H. pylori*) between the **BreathID® Hp System** results where breath is collected using **IDkit:Hp™ One** via a nasal cannula applying the 5 DOB threshold in pediatric subjects and stool antigen outcome or biopsy results in the pediatric population.
2. Overall agreement in diagnosis (presence/absence of *H. pylori*) between the **BreathID® Hp Lab System** results when analyzing **IDkit:Hp™ Two** breath sample bags using the 5 DOB threshold in pediatric subjects and the stool antigen outcome or biopsy results in the pediatric population.

14.2.3. *Study Hypotheses*

In this study, the following two sets of hypotheses will be evaluated for both the **IDkit:Hp One** used with the **BreathID® Hp System** and **IDkit:Hp™ Two** used with the **BreathID® Hp Lab System**.

- H_0 : Overall agreement $< 75\%$
- H_1 : Overall agreement $\geq 75\%$

14.3. *Sample Size*

The sample size for this study of pediatric subjects with indications for *H. pylori* testing is calculated to allow confirmation of both, the primary and secondary study endpoints. For the safety assessment, with no related SAE's expected, a sample size of 35 evaluable subjects would provide an upper confidence limit with less than or equal to 10% for the 95% two sided confidence limit. In order to support the efficacy endpoints a sample size is calculated through the width of the two-sided 95% confidence interval of the percent overall

Exalenz Bioscience Ltd.	Last update on: Mar. 12, 2017
Study Title: Clinical Study to Confirm Safety and Accuracy in Detection of H. pylori with ¹³C-Urea Breath Test using the BreathID® Hp and BreathID® Hp Lab Systems in the Pediatric Population	Protocol Number: PED-HP-0616B Version 2.0
Document No.: CSD00092	Page 45 of 59

agreement, such that the lower limit of the confidence interval will be greater than or equal to 75% with a point estimate of 90%.

A total of at least 40 evaluable subjects with no less than at least 5 positive subjects will be accrued for both breath collection methods. If the minimum of 5 positive subjects is not reached within the first 40 subjects enrolled, enrolment will continue until this minimal number of positive subjects is reached (with evaluable UBT results for both breath collection methods).

This will be sufficient to confirm the safety and the utility of the **BreathID® Hp System** and **BreathID® Hp Lab System** in detecting *H.pylori* infection in pediatric subjects.

Distribution of subject's ages will be monitored to assure all age ranges are represented, while predominantly (approximately 2/3) enrolling children under the age of 12.

14.4. Randomization

The study is an open label study, and is not randomized.

14.5. Analysis Sets

14.5.1. Full Analysis Set (FA)

The Full Analysis (FA) set includes all subjects who were enrolled and underwent study tests (**BreathID® Hp System** when using **IDkit:Hp™ One** nasal cannula and/or **BreathID® Hp Lab System** when using **IDkit:Hp™ Two** breath sample bags and stool antigen testing).

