12.6. Early Withdrawal from the Study

Subjects, their relatives, their representatives or the subjects' physician may withdraw the subject from the study at any time if they feel the study is not in the subjects' best interest, or they may be withdrawn by the investigator or sponsor for safety, compliance issues, or administrative reasons. All withdrawals will be fully documented as to time and cause.

If the subject or his/her legal guardian withdraws from the study and also withdraws consent for the disclosure of future information, no further evaluations should be performed and no additional data should be collected. This will not have any effect on the treatment that the subject receives. The subject's data that have been collected until the time of withdrawal will be retained and analyzed.

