13.1.3. Stool sample collection visit (Day 1 +/- 7 days)

1. The stool antigen test will be performed within 7 days before or after the UBT and after at least 2 weeks of refraining from proton pump inhibitors & H2 blockers and 4 weeks of refraining from antimicrobials and bismuth preparations. The test procedure is described in Appendix B.
2. Stool specimens will be sent to a central lab. The site coordinator will provide each subject with all supplies needed for collection of the stool specimen. The specimen will be either collected on-site, brought back to the site, brought to a local approved stool collection facility or it may be sent directly to a central laboratory from the subject's residence. A requisition form will be completed. After confirming that each stool antigen sample was sent to the central lab, the study coordinator will complete an entry line in a log documenting the shipment. The name and the address for the central laboratory service provider can be found in the respective documentation
3. Adverse events will be recorded, according to rules of assessment and documentation defined in Section 17 below).

The visit can be combined with the Breath Test visit and/or with the Screening visit and performed on the same day.

For each subject tested, an individual set of electronic Case Report Forms (CRFs) will be completed.

The Sponsor will notify the sites when to commence and stop recruitment.

Exalenz Bioscience Ltd.	Last update on: Mar. 12, 2017
Study Title: Clinical Study to Confirm Safety and Accuracy in Detection of H. pylori with ¹³C-Urea Breath Test using the BreathID® Hp and BreathID® Hp Lab Systems in the Pediatric Population	Protocol Number: PED-HP-0616B Version 2.0
Document No.: CSD00092	Page 41 of 59

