13.2. Screen failure Re-screening and dropout

Every subject for whom an Inform Consent/Accent Form was signed and withdrew from the study for any reason prior to the UBT or stool test will be defined as a *Screen Failure*.

Re-screening will be allowed once for each subject.

Exalenz Bioscience Ltd.	Last update on: Mar. 12, 2017
Study Title: Clinical Study to Confirm Safety and Accuracy in Detection of H. pylori with ¹³C-Urea Breath Test using the BreathID® Hp and BreathID® Hp Lab Systems in the Pediatric Population	Protocol Number: PED-HP-0616B Version 2.0
Document No.: CSD00092	Page 42 of 59

Every subject for whom an Inform Consent/Accent Form was signed and withdrew from the study for any reason after UBT and/or stool testing started will be defined as dropout/early termination. The cause of each such case will be recorded.

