14.6. Analysis set and their statistical analysis

The FA analysis set will serve as the analysis set for performance and safety assessments. The confirmatory performance assessment will also be performed on the PP analysis set.

Exalenz Bioscience Ltd.	Last update on: Mar. 12, 2017
Study Title: Clinical Study to Confirm Safety and Accuracy in Detection of H. pylori with ¹³C-Urea Breath Test using the BreathID® Hp and BreathID® Hp Lab Systems in the Pediatric Population	Protocol Number: PED-HP-0616B Version 2.0
Document No.: CSD00092	Page 46 of 59

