14.7.1. Safety Analysis

Any events related to study drug and/or device AE's rate will be presented along with a 95% exact binomial two sided 95% confidence interval. The analysis of all adverse events will include incidence tables and will include analyses by severity, relationship to device or drug and baseline variables.

Exalenz Bioscience Ltd.	Last update on: Mar. 12, 2017
Study Title: Clinical Study to Confirm Safety and Accuracy in Detection of H. pylori with ¹³C-Urea Breath Test using the BreathID® Hp and BreathID® Hp Lab Systems in the Pediatric Population	Protocol Number: PED-HP-0616B Version 2.0
Document No.: CSD00092	Page 47 of 59

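### The primary adverse event rate is computed on an analysis set that, on its natural reading, requires a stool test, so a dosed child without a stool sample is left out

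*Combined protocol and SAP*

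**What the plan says.** Section 14.2.1 makes the adverse event rate the primary endpoint. Section 14.6 assigns it to an analysis set: "The FA analysis set will serve as the analysis set for performance and safety assessments". Section 14.5.1 defines that set: "The Full Analysis (FA) set includes all subjects who were enrolled and underwent study tests". A parenthesis then lists the tests: the cannula system and/or the Lab System with "breath sample bags and stool antigen testing". The only other set, PP (section 14.5.2), is FA without major protocol deviations.

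The Safety Analysis section says that the related-event "rate will be presented along with a 95% exact binomial two sided 95% confidence interval". It names no other denominator.

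On timing, section 13.1.3 says: "The stool antigen test will be performed within 7 days before or after the UBT". On collection from the home, it says of the specimen that "it may be sent directly to a central laboratory". Section 13.2 foresees children who leave after dosing: withdrawal "after UBT and/or stool testing started will be defined as dropout/early termination". Section 12.6 says of a withdrawn subject that "data that have been collected until the time of withdrawal will be retained and analyzed".

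**The concern.** The study's main purpose is to show that children tolerate the dose. The population at risk is every child who ingested the solution, whether or not a stool sample followed. Stool matters only for the agreement endpoints.

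If membership of the safety set depends on a sample that may be collected days after dosing, it depends on something that happens after exposure and could be affected by how the child felt. Should children with events be less likely to supply stool, the primary rate would be too low. With about 40 children, one omitted event is enough to turn a non-zero rate into a reported zero.

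**Working it through.** **Who is in the FA set.** The parenthesis in 14.5.1 joins the two breath systems with and/or, then adds stool testing with a plain and. The change of connective favours this reading: (cannula and/or bags) and stool.

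**Can a dosed child lack stool?** Yes. Stool may follow the breath test by up to 7 days and may be sent from home (13.1.3), and withdrawal after the breath test is foreseen (13.2). Children whose stool was collected before or on the day of the breath test are not affected.

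**The plan's own safety figure.** Section 14.3 says that 35 evaluable subjects with no related serious events give an upper two-sided 95% limit of at most 10%. The exact upper limit for zero events is 1 − 0.025^(1/n).

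- n = 35: 10.003%
- n = 36: 9.74%
- n = 40 (the planned minimum): 8.81%

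The stated 35 is reproduced to rounding; the strict minimum is 36.

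**One child without stool, 41 dosed** (exact Clopper-Pearson upper limits):

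| Situation | FA set as written | All dosed |
|---|---|---|
| Only related event is in the omitted child | 0/40 = 0%, upper 8.81% | 1/41 = 2.4%, upper 12.86% |
| No related event in anyone | 0/40 = 0%, upper 8.81% | 0/41 = 0%, upper 8.60% |
| Only related event is in an included child | 1/40 = 2.5%, upper 13.16% | 1/41 = 2.4%, upper 12.86% |

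**More children without stool (assumed 3, 5, 8 or 10, with 40 in FA).** With one related event among those omitted, FA still reports 0/40 with an upper limit of 8.81%. The all-dosed results are:

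- 1/43 = 2.3%, upper 12.3%
- 1/45 = 2.2%, upper 11.8%
- 1/48 = 2.1%, upper 11.1%
- 1/50 = 2.0%, upper 10.6%

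**Expected bias.** Let p be the true related-event rate, qe the stool non-return rate in children with an event, and q0 that in children without one. The expected FA rate is p(1 − qe) / [p(1 − qe) + (1 − p)(1 − q0)]. Assume p = 5% and q0 = 10%, so that (1 − p)(1 − q0) = 0.95 × 0.90 = 0.855.

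- qe = 0%: 0.050/0.905 = 5.5%
- qe = 10%: 0.045/0.900 = 5.0% (no bias)
- qe = 30%: 0.035/0.890 = 3.9%
- qe = 50%: 0.025/0.880 = 2.8%

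The values of p, q0 and qe are assumptions; the documents give none of them.

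**The case against.** The strongest reply is that the parenthesis is a loose list of study tests, any of which qualifies a child, since the text never states that a missing stool result removes anyone. Other sections lean towards inclusion: 12.6 promises analysis of data collected before withdrawal, 17.1 records events from the start of the first test, and the Safety Analysis section plans incidence tables of all adverse events. The event would not disappear either, because discontinued subjects are listed (Disposition of Subjects) and serious events are reported within 24 hours (17.5). The group may be small, the 0/40 against 1/41 contrast is a worst case, and no decision turns on it: the General Considerations call the safety analysis descriptive, and the 10% in 14.3 is a planning precision for related serious events, not a pass/fail limit.

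Much of this stands. The loose reading is possible, the number affected is unknown, and the direction of any bias cannot be known from the documents. But none of the cited sections supplies another denominator for the rate and its interval. Section 12.6 names no analysis set and does not cover a child who stays in the study and never supplies stool. Section 13.2 adds to the confusion: withdrawal before the breath test or the stool test is a screen failure, so a dosed child who leaves before giving stool can fit both that label and the dropout label.

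**Conclusion.** The concern holds. Followed as written, on the natural reading of 14.5.1, the plan leaves a dosed child without a stool test out of the primary adverse event rate, and no other defined set brings that child back.

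The effect ranges from negligible to material. If non-return is unrelated to events, there is no bias, and with one omitted child the upper limit moves by only 0.2 to 0.3 percentage points. If the omitted child has the only related event, a rate of 2.4% with an upper limit of 12.9% is reported as zero with an upper limit of 8.8%. This rests on the stated reading of the definition and on at least one dosed child lacking stool. Because it concerns the denominator of the primary endpoint in a trial of about 40 children, it should be fixed before analysis.

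**What to change.** Add a Safety Analysis Set to section 14.5: all subjects who ingested any amount of the ¹³C-urea/citric acid solution, whether or not a breath or stool test was completed. State in 14.6 that safety is analysed on this set and that FA and PP serve the agreement analyses only. Agreement loses nothing, because the Handling of Missing Data section already excludes missing results.

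Reconcile 12.6 and 13.2 with the new definition, so that a dosed child cannot also count as a screen failure and the set used for data collected before withdrawal is named. Report the number of dosed subjects without a stool result in the disposition table.

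The cost is a few sentences in the statistical section and the two reconciled sections, with no new data or procedures. The reported rate may become slightly less or slightly more favourable.

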14.5.2. Per Protocol Analysis Set (PP)

The Per-Protocol (PP) analysis set includes all subjects from the FA analysis set without any major protocol deviation.

14.6. Analysis set and their statistical analysis

The FA analysis set will serve as the analysis set for performance and safety assessments. The confirmatory performance assessment will also be performed on the PP analysis set.

Exalenz Bioscience Ltd.	Last update on: Mar. 12, 2017
Study Title: Clinical Study to Confirm Safety and Accuracy in Detection of H. pylori with ¹³C-Urea Breath Test using the BreathID® Hp and BreathID® Hp Lab Systems in the Pediatric Population	Protocol Number: PED-HP-0616B Version 2.0
Document No.: CSD00092	Page 46 of 59

14.7. Statistical Analysis

14.7.1. General Considerations

Statistical analyses will be performed using SAS® v9.4 (SAS Institute, Cary NC, USA).

If any statistical tests are performed, they will be two-sided. The required significance level of findings will be equal to or lower than 5%. Where confidence limits are appropriate, the confidence level will be 95%.

Baseline values are defined as the last valid value prior to study start.

All statistical analyses of safety and performance measures will be descriptive in nature. Continuous variables will be summarized by a mean, standard deviation, minimum, median and maximum, and categorical variables by a count and percentage. Confidence intervals will be provided where relevant.

If multiple measurements are taken in a single subject, statistics described below will be appropriately modified to accommodate the within subject correlation.

14.7.2. Demographic and Other Baseline Characteristics

Demographic, medical and clinical history variables will be tabulated. Continuous variables will be summarized by a mean, standard deviation, minimum, median and maximum, and categorical variables by a count and percentage.

14.7.3. Disposition of Subjects

The numbers of subjects who were enrolled will be provided, as well as the reasons for all enrollment discontinuations, grouped by major reason (e.g., lost to follow-up, adverse event, poor compliance). A list of discontinued subjects, protocol deviations, and subjects excluded from the efficacy analysis will be provided as well.

14.7.1. Safety Analysis

Any events related to study drug and/or device AE's rate will be presented along with a 95% exact binomial two sided 95% confidence interval. The analysis of all adverse events will include incidence tables and will include analyses by severity, relationship to device or drug and baseline variables.

Exalenz Bioscience Ltd.	Last update on: Mar. 12, 2017
Study Title: Clinical Study to Confirm Safety and Accuracy in Detection of H. pylori with ¹³C-Urea Breath Test using the BreathID® Hp and BreathID® Hp Lab Systems in the Pediatric Population	Protocol Number: PED-HP-0616B Version 2.0
Document No.: CSD00092	Page 47 of 59

14.7.2. Confirmatory Efficacy Analyses

A 2x2 table of the results comparing the positive/negative results obtained from the **BreathID® Hp System** and for the results of the **BreathID® Hp Lab System** applying the 5 DOB threshold and the stool antigen test results will be presented (each system compared separately to the stool antigen testing).

The confirmatory efficacy analysis will present the estimation of overall agreement (%) on diagonal) with its two-sided 95% exact confidence intervals. If the lower limits of the two sided 95% confidence interval of the overall agreement are greater than or equal to 75%, the null-hypotheses will be rejected and we will have shown the breath test to be effective for the diagnosis of *H. pylori*. This will be performed for each breath collection method individually.

Positive and negative percent agreement will also be presented together with respective 95% confidence intervals.

Poolability of the data from the study sites will be assessed.

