Efficacy of the test can be fully extrapolated from the adult data (as confirmed with FDA through Pre-Submission Q170072). The goal of this study is thus primarily aimed to support expansion of the use of the ¹³C-urea and citric acid that is the subject of NDA-21-314, to the pediatric population (ages 3-18) and to confirm tolerance of the dose used for this target population. The ¹³C-urea and citric acid is contained in **IDkit:Hp™ One** (K130524) in the **BreathID® Hp System** and **IDkit:Hp™ Two** (K162150) in the **BreathID® Hp Lab System**. In addition to safety data that is collected for this study, their *H. pylori* status using the stool antigen test will also be collected as a comparator in order to further support

Exalenz Bioscience Ltd.	Last update on: Mar. 12, 2017
Study Title: Clinical Study to Confirm Safety and Accuracy in Detection of H. pylori with ¹³C-Urea Breath Test using the BreathID® Hp and BreathID® Hp Lab Systems in the Pediatric Population	Protocol Number: PED-HP-0616B Version 2.0
Document No.: CSD00092	Page 12 of 59

and confirm the efficacy of the breath test.

As mentioned above, EGD is not standard of care for evaluation of children with symptoms associated with *H. pylori* infection. They are evaluated for *H. pylori* infection most commonly with stool antigen testing. This study proposes to test the drug and its dosing in symptomatic children suspected of having *H. pylori* who will undergo both a breath test and an FDA cleared stool test. This population is chosen as they are the target population for the breath test and therefore drug use, and their evaluation with the stool test, will confirm that the use of this test is reasonable in the target population. Stool testing detects *H. pylori* antigen in stool specimens and can be used for diagnosis, therapeutic monitoring, and proof of eradication post treatment.

This study will use the Premier Platinum HpSA PLUS (K053335) Enzyme Immunoassay test kit for the detection of *H. pylori* antigen in human stool specimens (Appendix B). It will be tested in a central clinical laboratory.

The stool enzyme immunoassay employs a mixture of monoclonal anti-*H. pylori* antibodies as capture antibody and a mixture of peroxidase-conjugated monoclonal anti-*H. pylori* antibodies as detection antibody. Based on the intensity of color developed, results are reported as *H. pylori* antigen detected, not detected, or indeterminate.

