Exalenz Bioscience Ltd.	Last update on: Mar. 12, 2017
Study Title: Clinical Study to Confirm Safety and Accuracy in Detection of H. pylori with ¹³C-Urea Breath Test using the BreathID® Hp and BreathID® Hp Lab Systems in the Pediatric Population	Protocol Number: PED-HP-0616B Version 2.0
Document No.: CSD00092	Page 16 of 59

pediatrics.

Sample Size:

The sample size for this study of pediatric subjects with indications for *H. pylori* testing is calculated to allow confirmation of both, the primary and secondary study endpoints. For the safety assessment, with no related SAE's expected, a sample size of 35 evaluable subjects would provide an upper confidence limit with less than or equal to 10% for the 95% two sided confidence limit. In order to support the efficacy endpoints a sample size is calculated through the width of the two-sided 95% confidence interval of the percent overall agreement, such that the lower limit of the confidence interval will be greater than or equal to 75% with a point estimate of 90%.

A total of at least 40 evaluable subjects with no less than 5 positive subjects will be accrued for both breath collection methods. If the minimum of 5 positive subjects is not reached within the first 40 subjects enrolled, enrolment will continue until this minimal number of positive subjects is reached (with evaluable UBT results for both breath collection methods).

This will be sufficient to confirm the safety and the utility of the **BreathID® Hp System** and **BreathID® Hp Lab System** in detecting *H. pylori* infection in pediatric subjects.

Distribution of subject's ages will be monitored to assure all age ranges are represented, while at least two thirds (2/3) of the enrolled children will be under the age of 12.

Site Termination:

A study site may be terminated after appropriate consultation between the study sponsor and the principal investigator. Conditions warranting termination include, but are not limited to:

- Failure of the investigator to enroll subjects at an acceptable rate
- Insufficient adherence to protocol requirements

Exalenz Bioscience Ltd.	Last update on: Mar. 12, 2017
Study Title: Clinical Study to Confirm Safety and Accuracy in Detection of H. pylori with ¹³C-Urea Breath Test using the BreathID® Hp and BreathID® Hp Lab Systems in the Pediatric Population	Protocol Number: PED-HP-0616B Version 2.0
Document No.: CSD00092	Page 17 of 59

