comparing monoclonal enzyme immunoassay tests (EIA) and rapid immunochromatographic assays (ICA). The sensitivity and specificity of the tests analyzed had a high variation between 48.9%–92.2% and 88.9%–94.4%, respectively, depending on the test format. Best results were obtained for *Premier Platinum HpSA Plus* (which will be used in this study) with sensitivity and specificity of 92.2% and 94.4%, respectively. They conclude that EIA tests are more accurate compared to the currently available ICA-based test, that are fast and easy to use but provide less reliable results⁽¹⁴⁾. A recent meta-analysis conducted by Zhou and colleagues analyzed forty-five studies, including 5931 subjects, and evaluated the test performance of a *H. pylori* stool antigen test in children. The average sensitivity and specificity was 92.1% and 94.1%, respectively⁽¹⁵⁾. In a study conducted in South Korea on 515 subjects comparing the stool antigen test to histology, RUT, ¹³C-Urea breath test and serology, the accuracy of the stool antigen test ranged from 93% to 96%⁽¹⁶⁾. Furthermore, the available stool antigen tests have been shown to be able to distinguish infected from treated subjects^(17, 18), enabling the confirmation of treatment. Degradation of antigens in the intestine and consequent disintegration of epitopes might lead to false negative results. Moreover, the process of sample handling could be difficult for subjects. False negative results may occur when the bacterial load is low, due to proton-pump inhibitors or the recent use of antibiotics or bismuth^(19, 20). As such, there are limitations in eligibility criteria and study procedures in order to reduce the possibility of any potential effect by these factors⁽¹⁰⁾.

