9. STUDY DESIGN

Multi-center, non-randomized, open label study, designed to confirm the safety and the efficacy of ¹³C-urea breath test using the **BreathID® Hp** and the **BreathID® Hp Lab Systems** in pediatric subjects and confirm the efficacy of the respective means of breath collection, the nasal cannula and breath collection bags, in this population compared to *stool antigen* testing. A central lab will analyze the stool specimens. Children, that cannot inflate the breath collection bags, may perform UBT only with nasal cannula. All children will be exposed to non-radioactive ¹³C-urea and citric acid.

Subjects will be enrolled on a walk-in basis. Subjects will be treated only based on the established methods used in clinical practice. No patient management decisions should be made based on the investigational **BreathID® Hp** and/or **BreathID® Hp Lab Systems** test outcomes and the investigator and treating physician will remain blinded to the **BreathID® Hp** and/or **BreathID® Hp Lab System** test results until the end of the study.

Appropriate measures will be taken to maintain blinding.

A minimum of 40 evaluable, with at least 5 infected, subjects will be accrued. If the minimum of 5 positive subjects is not reached within the first 40 subjects enrolled, enrollment will continue until this minimal number of positive subjects is reached (with evaluable UBT results for both breath collection methods). The actual number of recruited subjects may be slightly higher due to parallel recruiting in multiple sites. The main eligibility criteria for the trial are subjects that have a clinical indication for *H. pylori* testing and are naïve to *H. pylori* treatment in the past 6 weeks.

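### Section 14.7.2 declares each breath test effective for diagnosis from overall agreement with stool antigen alone; with as few as 5 positives in 40, the negatives can carry that conclusion

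*Combined protocol and SAP*

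**What the plan says.** The hypotheses in 14.2.3 concern overall agreement only (below 75% against at least 75%), for each system separately. The objectives in 11.2 and the endpoints in 14.2.2 are also framed as overall agreement.

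The decision rule in Confirmatory Efficacy Analyses (14.7.2) has one condition: "If the lower limits of the two sided 95% confidence interval of the overall agreement are greater than or equal to 75" per cent. If it is met, "the null-hypotheses will be rejected and we will have shown the breath test to be effective for the diagnosis of" *H. pylori*. The same paragraph applies this to each collection method individually.

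PPA and NPA follow as reporting items: "Positive and negative percent agreement will also be presented together with respective 95% confidence intervals". No section gives them a threshold, a hypothesis or a part in the conclusion.

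On accrual, section 9 says: "A minimum of 40 evaluable, with at least 5 infected, subjects will be accrued". Section 14.3 adds: "If the minimum of 5 positive subjects is not reached within the first 40 subjects enrolled, enrolment will continue until this minimal number" is reached. Both the synopsis (Sample Size) and 14.3 then state of this sample: "This will be sufficient to confirm the safety and the utility of the" two systems in detecting infection in children.

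**The concern.** A test of overall agreement pools two groups of very different size. With 5 positives and 35 or more negatives, the result is almost entirely a statement about the negatives. If the fifth positive comes late, continued enrolment adds mostly more negatives. A diagnostic claim also needs the test to find the positives, and that is the part the rule does not examine.

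At stake is the sentence the trial is committed to writing. It could say that a system is effective for diagnosis beside a 2x2 table in which that system agreed with few of the stool-positive children. The sample-size statement about utility in detecting infection has the same gap.

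**Working it through.** **1. The plan's own figure.** Exact (Clopper-Pearson) lower limit for x agreements in n: the 0.025 quantile of Beta(x, n − x + 1). At the planning value of 90%, 36/40 gives 76.3%, so N = 40 meets the stated 75% target. 35/40 gives 73.2% and fails. The rule therefore allows 4 discordant results at N = 40. 38/43 gives 74.9% (fails) and 39/44 gives 75.4% (passes), so it allows 5 from N = 44 to 48.

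**2. The limiting case.** Take exactly 5 stool-positives and no discordant negatives.

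| N | Stool-positives concordant | Agreement | Lower limit | Rule | PPA (exact 95% CI) |
|---|---|---|---|---|---|
| 40 | 1 of 5 | 1 + 35 = 36/40 | 76.3% | met | 20% (0.5–71.6%) |
| 40 | 0 of 5 | 0 + 35 = 35/40 | 73.2% | not met | 0% (0–52.2%) |
| 44 | 0 of 5 | 0 + 39 = 39/44 | 75.4% | met | 0% (0–52.2%) |

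Even 5 of 5 concordant gives a PPA interval of 47.8–100%.

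**3. From stool agreement to infection.** Section 4.2 gives the chosen stool kit "sensitivity and specificity of 92.2% and 94.4%, respectively", from an adult study. Assumptions: the errors of the two tests are independent, breath specificity is 97% (range 90–100%), every enrolled child is evaluable by both methods, and the stool-positive rate r is 10%, 12.5%, 20% or 30%. The plan gives no rate; section 4.1 says US paediatric rates are not known.

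- True prevalence: π = (r − 0.056) / (0.922 + 0.944 − 1).
- Share of stool-positives infected: a = 0.922π / r. This is the expected PPA of a perfect breath test.
- Share of stool-negatives uninfected: b = 0.944(1 − π) / (1 − r).
- Breath sensitivity 50%, specificity s: PPA = 0.5a + (1 − s)(1 − a); NPA = sb + 0.5(1 − b).

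Worked at r = 12.5%: π = 0.069 / 0.866 = 0.080; a = 0.588; b = 0.993; PPA = 0.294 + 0.03 × 0.412 = 0.306; NPA = 0.963 + 0.004 = 0.967.

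**4. Pass probability under the enrolment rule.** If 40 children include at least 5 positives, N = 40 with a binomial number of positives. Otherwise N is the child who supplies the fifth positive (negative binomial). Agreements are Bin(positives, PPA) + Bin(negatives, NPA), compared with the minimum needed at that N.

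| Stool-positive rate | P(fewer than 5 in 40) | Mean N | Perfect breath test: expected PPA | Half of infections detected: P(rule met), range for specificity 90–100% |
|---|---|---|---|---|
| 10% | 62.9% | 53.7 | 47% | 62% (26–78%) |
| 12.5% | 42.9% | 46.6 | 59% | 51% (17–69%) |
| 20% | 7.6% | 40.6 | 77% | 25% (7–39%) |
| 30% | 0.3% | 40.0 | 87% | 8% (2–13%) |

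Substituting the paediatric meta-analysis figures in section 4.2 (92.1% and 94.1%) in the same formulas gives 61%, 50%, 24% and 7% at specificity 97%, so the choice of stool figures matters little.

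**The case against.** Much of the case on the other side stands. Efficacy is a secondary endpoint; the synopsis says "Efficacy of the test can be fully extrapolated from the adult data" and records FDA's confirmation. General Considerations (14.7.1) calls all safety and performance analyses descriptive. Section 4.3 reports breath-test sensitivity of 90–100%, so nothing in the documents suggests that a system would detect only half of infections. The 2x2 table, PPA, NPA and their intervals will sit beside the conclusion. These points reduce the consequence. They do not make the sentence follow from the test, because 14.7.2 says that this trial's result will have shown effectiveness.

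A reader might infer that the rule passes a test that misses four of five infected children. The documents do not support that. Stool-positive is not the same as infected: at a 12.5% rate, a perfect breath test would agree with at most 1 of 5 stool-positives about 10% of the time under the model above. A reader might also want a PPA threshold. With 5 positives, a perfect breath test would reach 4 of 5 only about 15%, 32% and 67% of the time at rates of 10%, 12.5% and 20%, so a threshold could reject a good test.

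Finally, the plan does not name the test that defines *positive* (section 9 says infected). Stool-positive is the natural reading, since stool is the comparator. If breath-positive were meant, the 1-of-5 case could not arise with only 5 positives; the conclusion would still rest on overall agreement alone.

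**Conclusion.** The point holds as a mismatch between what is tested and what is concluded. Overall agreement of at least 75% does not by itself show effectiveness for diagnosis or utility in detecting infection. With the minimum of 5 positives, the negatives can satisfy the rule almost alone.

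The size depends strongly on the stool-positive rate. For a system detecting half of infections, the chance of passing runs from about 62% at a 10% rate to about 8% at 30%, given independent errors, the stool accuracy in section 4.2 and 97% breath specificity. The 1-of-5 and 0-of-5 cases show what the rule permits; they are not predictions, and they require every negative to be concordant. Low PPA against stool is not by itself evidence of missed infection. Severity is minor to should-fix: the wording overstates a secondary result, and correcting it changes what the trial may conclude.

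**What to change.** In Confirmatory Efficacy Analyses (14.7.2), keep the rule and replace the claim of effectiveness for diagnosis with:

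> *overall agreement with stool antigen testing of at least 75% has been shown for that system; this conclusion will be stated together with the number of stool-positive subjects and PPA and NPA with exact 95% confidence intervals.*

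In the Sample Size text of the synopsis and in 14.3, replace the phrase on utility in detecting infection with: *to assess overall agreement of each system with stool antigen testing*. Add that with only 5 comparator-positive subjects PPA is imprecise: even 5/5 gives an exact 95% interval of 47.8–100%.

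This edit should leave the accrual definition of *positive* as it stands and should add no PPA threshold.

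The cost is a less favourable stated conclusion in three places. The decision rule, sample size and analyses do not change, and PPA, NPA and their intervals are already planned.
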